10.2.2.2. Reporting Period for Adverse Events

Following initiation of study drug, collect all AEs, regardless of cause or relationship, until 30 days after last administration of study drug and report the AEs on the eCRFs as instructed.

All AEs and clinically significant laboratory abnormalities should be followed until resolution or until the AE is stable, if possible. Gilead may request that certain AEs be followed beyond the protocol-defined follow-up period.

10.2.2.3. Reporting Period for Serious Adverse Events

All SAEs, regardless of cause or relationship, that occur after the subject first consents to participate in the study (ie, signing the informed consent form) and throughout the duration of the study, including the Safety Follow-up visits, must be reported on the applicable eCRFs and to Gilead Global Patient Safety. This also includes any SAEs resulting from protocol-associated procedures performed after the informed consent form is signed.

Any SAEs (including deaths; see Section 10.2.3 for exclusions) that occur during the study (including the Safety Follow-up visits detailed in the Schedule of Assessments [Table 1]) or within 30 days of the last dose of study drug or initiation of alternative therapy, whichever is later, should also be reported regardless of causality.

Investigators are not obligated to actively seek SAEs after the protocol-defined follow-up period; however, if the investigator learns of any SAEs that occur after the protocol-defined follow-up period has concluded and the event is deemed relevant to the use of study drug, the investigator should promptly document and report the event to Gilead Global Patient Safety.

10.2.2.4. Reporting Period for Special Situation Reports

All study drug SSRs that occur from study drug initiation and throughout the duration of the study, including the Safety Follow-up visits, must be reported to the sponsor.

10.2.2.5. Adverse Event Collection and Documentation

Adverse Events Reporting Process

It is the responsibility of the Investigator to document all AEs that occur during the study. All adverse events regardless of seriousness, severity, or relationship to the study drug, that occur during the safety reporting period, must be recorded in the AE page of the eCRF. AEs should be elicited by asking the subject a non-leading question (eg, “have you experienced any new or changed symptoms since we last asked/since your last visit?”). AEs can also represent abnormal findings from laboratory tests and other study procedures. The Investigator must review all laboratory and test data; abnormal findings should be assessed to determine if they meet the criteria for adverse events (Section 10.2.1.1, Section 10.2.2.8).

For all AEs, the Investigator must pursue and obtain information adequate to assess whether it meets the criteria for classification as an SAE and, therefore, requires immediate notification to the sponsor or its designee (Section 10.2.5). In addition, sufficient information must be obtained by the Investigator to perform a causality assessment, which must be done for every adverse event. Follow-up by the Investigator is required until the event or its sequelae resolve or stabilize, as assessed by the Investigator. The outcome of each AE must be provided on the eCRF.

To assist in the sponsor’s assessment of each case, further information may be requested from the Investigator to provide clarity and understanding of the event in the context of the clinical study.

Adverse events and SAEs resulting from SSRs must be reported in accordance with the AE and SAE reporting guidance summarized in Sections 10.2.2.5 and 10.2.5.

Serious Adverse Events Reporting Process

SAEs are to be recorded on the eCRF and SAE form. The SAE form must be forwarded to the sponsor or the sponsor's designee in accordance with the timelines summarized in Section 10.2.5. The Investigator should include a detailed description of the event(s), including the clinical course, criteria for seriousness, treatments administered, action taken with respect to study drug, rationale for the Investigator's assessment, including causality, and other relevant information, such as possible alternative etiologies.

Information captured on both the SAE form and entered into the eCRF should be consistent.

Special Situation Reporting Process

All SSRs will be recorded on the special situation report form and forwarded to the sponsor or sponsor's designee in accordance with the timelines summarized in Section 10.2.5.

10.2.2.6. Assessment of Adverse Event Severity

The severity of AEs will be graded using NCI CTCAE v5.0. For each SAE, the highest severity grade should be reported. If a CTCAE criterion does not exist, the Investigator should assess the severity according to the criteria in Table 3.

Table 3. Grading for Adverse Events Not Listed in NCI-CTCAE

CTCAE Grade	Severity	Definition
Grade 1	Mild	Asymptomatic or mild symptoms; clinical or diagnostic observations only; intervention not indicated
Grade 2	Moderate	Minimal, local or noninvasive intervention indicated; limiting age-appropriate instrumental ADL ¹
Grade 3	Severe	Severe or medically significant but not immediately life-threatening; hospitalization or prolongation of existing hospitalization indicated; disabling; limiting self-care ADL ^{2,3}
Grade 4	Life-threatening	Life-threatening consequences; urgent intervention indicated ³
Grade 5	Death	Results in death ³

¹ Instrumental ADL refers to preparing meals, shopping for groceries or clothes, using the telephone, managing money, etc.

² Self-care ADL refer to bathing, dressing and undressing, feeding self, using the toilet, taking medications, and not bedridden.

³ These events should be assessed to determine if they meet the definition of SAEs.

ADL = activities of daily living; NCI-CTCAE = National Cancer Institute common terminology criteria for adverse events; SAE = serious adverse event.

10.2.2.7. Assessment of Adverse Event Causality

The Investigator's causality assessment is required for all AEs including both non-serious and serious AEs. The causality assessment is the determination of whether there exists a reasonable possibility that the study treatment caused or contributed to an AE. In order to determine causality, the Investigator should consider the temporal relationship of the onset of the event to the start of study drug; the course of the event and, in particular, whether the event resolves or improves with dose reduction or study drug discontinuation; the known toxicities of the study drug; events expected to occur in subjects with the disease under study; and concomitant medications and comorbidities that may have a known association with the event. Causality is to be assessed as follows:

- Related: Plausible time relationship to study treatment administration; plausible time relationship of improvement or resolution with study drug dose reduction or discontinuation; event cannot be explained by the underlying disease, comorbidities, or concomitant medications.
- Possibly related: a reasonable time sequence to administration of study drug, but which could also be explained by the underlying disease, comorbidities, or concomitant medications.
- Unlikely related: a temporal relationship to drug administration that makes a causal relationship improbable and the underlying disease, comorbidities, or concomitant medications provide a plausible explanation.
- Not related: a causal relationship to the study drug can be easily ruled out.

10.2.2.8. Adverse Events Based on Abnormal Test Findings

An abnormal test finding that meets any one of the criteria below should be considered an AE:

- Test result is associated with accompanying symptoms.
- Test result requires additional diagnostic testing or medical/surgical intervention.
- Test result leads to a change in study treatment dosing (eg, dose modification, interruption, or permanent discontinuation) or concomitant drug treatment (eg, addition, interruption, or discontinuation) or any other change in a concomitant medication or therapy
- Test result leads to any of the outcomes included in the definition of an SAE. (Note: This would be reported as an SAE, Section 10.2.5)
- Test result is considered an AE by the Investigator.

Laboratory results that fall outside the reference range and do not meet one of the criteria above should not be reported as AEs. Repeating an abnormal test, in the absence of the above conditions, does not constitute an AE. Any abnormal test result that is determined to be an error does not require reporting as an AE.

Any abnormal test finding that meets the criteria for an SAE (Section [10.2.1.2](#)) should be reported as such.

10.2.2.9. Disease Progression

Disease progression should not be reported as an AE. It is important to differentiate expected disease progression from an AE. Events that are clearly consistent with the expected pattern of disease progression should not be considered AEs. Expected disease progression refers to an event that is unequivocally related to disease progression, and that the clinical course is consistent with what would be expected for the subject's disease. A clinical event in the setting of disease progression would be considered an AE if it could not unequivocally be attributed to or consistent with expected disease progression.

Hospitalization due to signs and symptoms of disease progression (as defined above) should not be reported as an SAE.

10.2.3. Reporting Deaths

Death is an outcome of an SAE and not, in itself, an SAE. When death is an outcome, the event(s) resulting in death should be reported (eg, "pulmonary embolism" with a fatal outcome). The appropriate diagnosis (ie, cause of death) should be recorded and assigned severity Grade 5. The time period for reporting AEs (including fatal AEs) continues up to 30 days after the last dose of study drug or initiation of alternative therapy, whichever is later. Deaths that occur more than 30 days after the last dose of study drug or initiation of alternative therapy, whichever is later, are to be reported if they are assessed by the Investigator as related to study drug. Fatal AEs meeting these criteria are SAEs and should be reported to the sponsor or the sponsor's designee in accordance with the timelines specified in Section [10.2.5](#).

Deaths related to progression of the underlying disease during the study will not be reported as an SAE (see Section [10.2.2.9](#)) if, in the Investigator's judgment, the event is unequivocally due to the expected course of progression of the underlying disease, and not due to another cause.

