4.3. Study Procedures

Enrollment occurs upon completion of all screening procedures. Enrollment will be performed centrally by an interactive web response system (IWRS). Clear documentation as to the reason the subject was not dosed should be provided on the relevant eCRF. Unless otherwise specified, collection windows for laboratory assessments prior to dosing may be obtained up to 3 days prior to dosing. Treatment (dosing) may be permitted either 1 day before or within 7 days after scheduled visits.

An infectious disease pandemic may pose additional risks to study drug availability, the study visit schedule, and adherence to protocol-specified safety monitoring or laboratory assessments. Refer to [Appendix 2](#) for further details on the risks and risk mitigation strategy.

For safety parameters, please refer to Section [10.1](#).

Table 1. Schedule of Assessments

Phase	Pre-Treatment	Treatment			Unscheduled Visit	End of Treatment ^a	Safety Follow-up ^b	End of Study ^a
		Treatment Cycle 1 through Last Cycle (21-day cycle)		Day 8				
Period	Screening	Day 1 (includes baseline C1D1)	Day 8					
Day	Days -21 to 1							
Informed consent	X							
Inclusion and exclusion criteria	X							
Prior sacituzumab govitecan parent study	X							
Weight		X						
Hematology ^c		X	X	X	X	X		
Serum chemistry ^d		X	X	X	X	X		
Urine pregnancy test ^e	X	X		X	X	X	X	X
FSH ^f	X							
Sacituzumab govitecan administration		X	X					
Concomitant medications		Throughout Study						
SAEs ^g		Throughout Study						
AEs ^g		Throughout Study						

AE = adverse event; C1D1= Cycle 1 Day 1; FSH = follicle-stimulating hormone; SAE = serious adverse event

a End of treatment (EOT) visit approximately 30 days of the last dose of the study drug. For the definition of End of Study (EOS), refer to Section 3.6.

b For subjects of childbearing potential, the Safety Follow-up visits will be every 28 days for 6 months after study drug discontinuation. For subjects of non-childbearing potential who have ongoing AEs or SAEs at EOT, the Safety Follow-up visits will be every 6 weeks for up to 6 months after study drug discontinuation or until the criteria for EOS (Section 3.6) have been met. Subjects of non-childbearing potential who do not have ongoing AEs or SAEs at EOT will be considered as having reached EOS.

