6.4. Death

All-cause deaths will be summarized (including presentation of causes of death), and deaths within 30 days of the last dose of study drug will be summarized. A listing of all death information will be generated.

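### Protocol 10.2.3 ties reporting of late deaths to relatedness within a follow-up period where 10.2.2.3 requires all SAEs, which exposes late fatal SAEs and the SAP's causes of death

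*Protocol*

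**What the plan says.** Protocol 10.2.2.3, first paragraph, sets the general rule. It covers "All SAEs, regardless of cause or relationship, that occur after the subject first consents to participate in the study" and, continuing, "throughout the duration of the study, including the Safety Follow-up visits, must be reported on the applicable eCRFs". It states no exception. The second paragraph repeats the duty whatever the causality, and on deaths it adds a pointer: "Any SAEs (including deaths; see Section 10.2.3 for exclusions) that occur during the study". The third paragraph covers the time after protocol-defined follow-up, when only SAEs that come to the investigator's notice and are thought relevant to study drug need reporting.

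Protocol 10.2.3 has two limiting rules on deaths:
- Late deaths: the rule reaches "Deaths that occur more than 30 days after the last dose of study drug or initiation of alternative therapy, whichever is later". Its condition for this group is that such cases "are to be reported if they are assessed by the Investigator as related to study drug".
- Progression deaths: "Deaths related to progression of the underlying disease during the study will not be reported as an SAE", provided the investigator considers the event unequivocally due to the expected course of the disease.

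The length of follow-up is in the notes to Protocol Table 1 (Section 4.3): "For subjects of childbearing potential, the Safety Follow-up visits will be every 28 days for 6 months after study drug discontinuation". Subjects of non-childbearing potential with ongoing AEs or SAEs at End of Treatment (EOT) are seen every 6 weeks for up to 6 months. The remainder reach End of Study (EOS) at EOT, about 30 days after last dose.

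SAP 6.4 plans this display: "All-cause deaths will be summarized (including presentation of causes of death"), together with a separate summary of deaths within 30 days of last dose and a listing of death information. It names no data source and no cut-off for the all-cause summary.

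**The concern.** For a subject in Safety Follow-up the two protocol sections can give different answers about the same death. Under 10.2.2.3 an unrelated fatal SAE is reported. Under 10.2.3, read literally, it need not be once the 30-day or alternative-therapy window has passed.

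Long-term safety is the study's only objective. If late fatal events reach the sponsor only when the investigator calls them related, then reporting in an open-label study depends on a subjective call, and it depends on the attribute the sponsor would want to review. The same call may decide whether a cause is recorded for SAP 6.4. Protocol 10.2.2.7 adds to the difficulty: it has separate categories for related and possibly related, and 10.2.3 does not say whether the second qualifies.

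**Working it through.** The documents state no figure to reproduce. The check is a comparison of texts, with one short calculation of the overlap.

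1. **Is there a conflict?** Take an unrelated sepsis starting on day 90 after last dose, in a subject still in Safety Follow-up who has had no alternative therapy. If it is not fatal, 10.2.2.3 requires a report. If it is fatal, the first paragraph of 10.2.2.3 still requires a report, because a fatal outcome is the first seriousness criterion in 10.2.1.2. The late-death rule in 10.2.3 asks for a report only on condition of relatedness.

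2. **Does the pointer settle it?** The pointer in 10.2.2.3 refers to exclusions. The only sentence in 10.2.3 worded as an exclusion is the one on progression deaths. The late-death sentence is worded as a condition for reporting. If the pointer covers both, the fatal sepsis is left out while the non-fatal one is reported. If it covers only progression deaths, the late-death sentence contradicts 10.2.2.3 for anyone still in follow-up. The text does not choose between these readings.

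3. **How long is the overlap?** Inputs: 6 months of Safety Follow-up (Table 1 notes), a 30-day window (10.2.3), and the SAP's conversion of 30.4375 days per month (SAP 6.1).
   - Follow-up: 6 × 30.4375 = 182.6 days.
   - Overlap: 182.6 − 30 = 152.6 days. With 30-day months it is 180 − 30 = 150 days.
   - Share of the period after last dose: 152.6 / 182.6 = 84%.
   - This is a maximum. A later start of alternative therapy moves the unconditional window out and shortens the overlap. So does leaving the study once AEs have resolved or stabilized (Protocol 5.4).
   - For subjects who reach EOS at EOT, the overlap is zero on-study days.

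4. **Which outputs are touched?**
   - All-cause count: death is the first study-discontinuation criterion in Protocol 5.4. Meeting a 5.4 criterion requires an EOS eCRF (3.6) with no causality condition, and SAP 5.3 tabulates discontinuation reasons. On-study deaths can therefore be counted whatever their cause.
   - 30-day death summary and TEAE tables (Protocol 11.3.3, SAP 6.2 and 6.4): these end 30 days after last dose, inside the unconditional window, so they are unaffected.
   - Cause of death: the one place that tells the site to record it is 10.2.3, as part of reporting the fatal event. Nothing says that the EOS eCRF has a cause field.
   - SAE reports of late unrelated fatal events: directly affected.

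5. **How many deaths?** This cannot be computed. The documents give neither a death rate nor the share of subjects entering Safety Follow-up.

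**The case against.** The strongest reply is that the sections can be read together. 10.2.2.3 expressly sends the reader to 10.2.3 for deaths. 10.2.3 treats death as an outcome and not as an SAE in itself, and it never says that only related late deaths are reported. Its late-death sentence could then be the rule for the time after follow-up ends, matching the third paragraph of 10.2.2.3. For subjects who reach EOS at about day 30 that fits exactly. This reading is available and may be what was intended. It is not written down, however: the sentence counts from last dose or alternative therapy, not from the end of follow-up, and a site could apply it as it stands.

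Second, subjects followed because of ongoing AEs or SAEs have those events followed to resolution or stabilization, and 10.2.2.5 requires an outcome for each AE. A fatal outcome of an event already open should therefore be recorded whatever its causality. That stands, and it narrows the gap to events that begin during follow-up.

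Third, the eCRF is not among the documents, and the listing of death information in SAP 6.4 is consistent with a separate death form that includes cause. That is possible. The point is that the protocol does not require it.

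A reader might go further and infer that the whole all-cause death summary rests on a set filtered by causality, or that the share of deaths called related would be inflated by a known amount. The documents do not support either. The EOS eCRF captures on-study deaths without regard to cause, and no death counts are given from which to size a distortion.

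**Conclusion.** The point holds in limited form. Protocol 10.2.2.3 and 10.2.3 set different conditions for reporting deaths in Safety Follow-up, and the cross-reference leaves the intended exclusion unclear. At its widest the overlap is about 150 days per subject, assuming the full 6 months of follow-up and no later start of alternative therapy. What is exposed is SAE reporting of late, unrelated fatal events and the presentation of causes in SAP 6.4. The second part assumes that no other eCRF page collects cause of death; if one does, only SAE reporting is affected. No primary endpoint is shown to change. The correction is still worth making, because it is cheap and the present text lets a subjective causality call decide whether a late fatal event reaches the sponsor.

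**What to change.** - In Protocol 10.2.3, apply the relatedness condition to deaths after the subject's protocol-defined follow-up has ended, in line with the third paragraph of 10.2.2.3. Have the pointer in 10.2.2.3 name the exclusion it means.
- Keep the existing rule that deaths unequivocally due to progression are not reported as SAEs.
- Require the date and primary cause of every death up to EOS on the eCRF. This also gives progression deaths, which stay outside SAE reporting, a stated place for their cause.
- In SAP 6.4, name that record as the source and EOS as the cut-off for the all-cause summary. SAP Section 1 says the SAP is based on the original protocol of 16Dec2019, so its alignment with the current 10.2.3 should be confirmed at the same time.

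The cost is a sentence or two in an amendment, a matching line in the SAP, and a few extra death or SAE forms. No visits are added, since these subjects are already being contacted.

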10.2.4. Pregnancy Reporting Process

The investigator should report pregnancies in female study subjects that are identified after initiation of study drug and throughout the study (including through the protocol-required Safety Follow-up visits) or 6 months after the last study drug dose, whichever is longer, to Gilead Global Patient Safety using the pregnancy report form within 24 hours of the Investigator becoming aware of the pregnancy.

The investigator should report pregnancies in female partners of male subjects that are identified after initiation of study drug by the male subject and throughout the study (including through the protocol-required Safety Follow-up visits), or 3 months after the last study drug dose, whichever is longer, to Gilead Global Patient Safety using the pregnancy report form within 24 hours of the Investigator becoming aware of the pregnancy.

Contact details for transmitting the pregnancy report form are as follows:

Gilead Global Patient Safety
Email: [contact]
or
[contact]

The pregnancy itself is not considered an AE, nor is an induced elective abortion to terminate a pregnancy without medical reasons.

All other premature terminations of pregnancy (eg, a spontaneous abortion, an induced therapeutic abortion due to complications or other medical reasons) must be reported within 24 hours as an SAE, as described in Section 10.2.5. The underlying medical reason for this procedure should be recorded as the AE term.

A spontaneous abortion is always considered to be an SAE and will be reported as described in Section 10.2.5. Furthermore, any SAE occurring as an adverse pregnancy outcome after the study must be reported to Gilead Global Patient Safety.

The subject should receive appropriate monitoring and care until the conclusion of the pregnancy. The outcome of the pregnancy/partner pregnancy should be reported to Gilead Global Patient Safety using the pregnancy report form. If the end of the pregnancy/partner pregnancy occurs after the study has been completed, the outcome should be reported directly to Gilead Global Patient Safety. Gilead Global Patient Safety contact information is as follows: email: [contact] and [contact].

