3.4. End of Treatment

After discontinuation of treatment (See Section [5.3](#)), all subjects must complete an end of treatment (EOT) visit approximately 30 days after the last dose of the study drug. Data should be entered into the EOT electronic case report form (eCRF).

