3.6. End of Study

The end of the study will be the date of the last visit/contact/follow-up in the study. An End of Study (EOS) visit must be performed and entered into the EOS eCRF if the criteria cited in Section 5.4 have been met. The EOS visit can be performed by telephone.

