Appendix 3. Cockcroft-Gault Formula

$C_{Cr} = [(140 - \text{age}) \times \text{weight}] / (72 \times S_{Cr}) \times 0.85$ (if female)

Abbreviations/ Units

C_{Cr} (creatinine clearance) = mL/minute

Age = years

Weight = kg

S_{Cr} (serum creatinine) = mg/dL

{Cockcroft 1976}

Appendix 4. Pregnancy Precautions, Definition for Female of Childbearing Potential, and Contraceptive Requirements

1) Definitions

a. Definition of Childbearing Potential

For the purposes of this study, a female-born subject is considered of childbearing potential following the initiation of puberty (Tanner stage 2) until becoming postmenopausal unless the subject is permanently sterile or has medically documented ovarian failure.

Women are considered to be in a postmenopausal state when they are at least 54 years of age with cessation of previously occurring menses for at least 12 months without an alternative cause. In addition, women younger than 54 years with amenorrhea of at least 12 months also may be considered postmenopausal if their FSH level is in the postmenopausal range and they are not using hormonal contraception or hormonal replacement therapy.

Permanent sterilization includes hysterectomy, bilateral oophorectomy, or bilateral salpingectomy in a female subject of any age.

b. Definition of Male Fertility

For the purposes of this study, a male-born subject is considered fertile after the initiation of puberty unless the subject is permanently sterile by bilateral orchidectomy or medical documentation.

2) Contraception Requirements for Female Subjects

a. Study Drug Effects on Pregnancy and Hormonal Contraception

Sacituzumab govitecan is contraindicated in pregnancy because a malformative effect has been demonstrated/suspected or is unknown, taking into consideration class effects and genotoxic potential. Based on the assessment of published data related to CYP450 enzyme inhibition and induction experiments for SN-38, efficacy of hormonal contraception is not expected to be impacted due to sacituzumab govitecan administration. A dedicated oral contraceptive drug-drug interaction clinical study has not been conducted. Refer to the latest version of the investigator's brochure for additional information.

b. Contraception Requirements for Female Subjects of Childbearing Potential

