- e) Sponge with spermicide

Inclusion of methods of contraception in this list of permitted methods does not imply that the method is approved in any country or region. Methods should only be used if locally approved.

Female subjects must also refrain from egg donation, cryopreservation of germ cells, and in vitro fertilization during treatment and until the end of contraception requirement. Female subjects should be advised to seek advice of the Investigator about egg donation and cryopreservation of germ cells before treatment.

3) Contraception Requirements for Male Subjects

It is theoretically possible that a relevant systemic concentration of study drug may be achieved in a female partner from exposure of the male subject's seminal fluid and poses a potential risk to an embryo/fetus. Therefore, male subjects with female partners of childbearing potential must use condoms during treatment and until 6 months after the last dose of study drug. If the female partner of childbearing potential is not pregnant, additional highly effective contraception recommendations should also be considered.

Male subjects must also refrain from sperm donation, and/or cryopreservation of germ cells during treatment and until the end of contraception requirement. Male subjects should be advised to seek advice of the Investigator about sperm donation and cryopreservation of germ cells before treatment.

4) Unacceptable Birth Control Methods

Birth control methods that are unacceptable include periodic abstinence (eg, calendar, ovulation, symptothermal, postovulation methods), withdrawal (coitus interruptus), spermicides only, and lactational amenorrhea method. A female condom and a male condom should not be used together.

5) Procedures to be Followed in the Event of Pregnancy

Female subjects will be instructed to notify the Investigator if they become pregnant or suspect they are pregnant at any time from start of the study and throughout the study (including the post study drug follow-up period) or 6 months after the last dose of study drug, whichever is longer. Sacituzumab govitecan must be discontinued immediately upon consultation with the medical monitor.

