Male subjects whose partner has become pregnant or suspects she is pregnant from start of study and throughout the study (including the post study drug follow-up period) or 3 months after the last dose of study drug, whichever is longer, must also report the information to the investigator. Instructions for reporting pregnancy, partner pregnancy, and pregnancy outcome are outlined in Section 10.2.4.

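### Partner pregnancies are reportable to a floor of only 3 months after a man's last dose, while condoms are required for 6 months; how many men this affects depends on how 'throughout the study' is read

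*Protocol*

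**What the plan says.** **Contraception, men.** Protocol Appendix 4 item 3 says that men with partners of childbearing potential "must use condoms during treatment and until 6 months after the last dose of study drug". The reason given is possible harm to an embryo or fetus through seminal fluid. Agreeing to Appendix 4 contraception is an inclusion criterion (Section 5.1, item 5).

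**Reporting, men.** Section 10.2.4 has the investigator report partner pregnancies identified from the start of study drug and throughout the study, including any required Safety Follow-up visits, "or 3 months after the last study drug dose, whichever is longer". Appendix 4 item 5 sets the same limit for the man himself: throughout the study "or 3 months after the last dose of study drug, whichever is longer, must also report the information to the investigator".

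**Women.** Contraception (Appendix 4 item 2b) runs to 6 months after the last dose. Notification (Appendix 4 item 5) and reporting (Section 10.2.4) run throughout the study or to 6 months, whichever comes later.

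**When the study ends.** Section 3.6 points two ways. It defines a trial-wide date: "The end of the study will be the date of the last visit/contact/follow-up in the study". It also provides an individual visit, tied to the subject-level criteria of Section 5.4: "An End of Study (EOS) visit must be performed and entered into the EOS eCRF". All subjects "must complete an end of treatment (EOT) visit approximately 30 days after the last dose of the study drug" (Section 3.4). Footnote b of the Schedule of Assessments (Section 4.3, Table 1) then states: "Subjects of non-childbearing potential who do not have ongoing AEs or SAEs at EOT will be considered as having reached EOS".

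**The concern.** The protocol asks men to take a precaution for 6 months but may stop asking about its failure at 3. On the per-subject reading, a partner pregnancy first identified in months 4 to 6 can fall outside the rule written for partner pregnancies. The man's duty to tell the investigator has also ended, although he must still use condoms. The female rules show no such mismatch, and the documents give no reason for the shorter male figure.

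What would be lost is a small amount of safety information: first notice of partner pregnancies, especially uncomplicated ones, in a period that the protocol itself treats as needing precaution. No endpoint or analysis is at stake.

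**Working it through.** There is no planned figure to reproduce; the check compares time windows. Months are converted at 30.4375 days, the factor in SAP Section 6.1.

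**Inputs**
- Condom period, men: 6 months = 6 × 30.4375 = 182.6 days after the last dose (Appendix 4 item 3).
- Reporting floor, men: 3 months = 3 × 30.4375 = 91.3 days (Section 10.2.4; Appendix 4 item 5).
- End-of-treatment (EOT) visit: about day 30 (Section 3.4).
- Safety Follow-up of subjects not of childbearing potential with ongoing AEs or SAEs: every 6 weeks, for up to 6 months or until EOS criteria are met (Table 1, footnote b). Section 5.4 item 4 ends participation after treatment once AEs are resolved or stable.

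**Step 1: where men fall in footnote b.** Appendix 4 item 1a defines the term for women only: "a female-born subject is considered of childbearing potential following the initiation of puberty". Men have a separate fertility definition in item 1b. So men enter Safety Follow-up only because of ongoing AEs or SAEs, and only until those settle.

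**Step 2: per-subject reading.** Let E be the day of a man's own EOS, counted from his last dose.

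Reporting window = max(E, 91.3). Shortfall = 182.6 − max(E, 91.3) when E is below 182.6, otherwise 0.

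For the rows after the first, I assume that the 6-weekly visits are counted from EOT and that EOS is declared at a visit.

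| Man's situation | E (day) | Window (day) | Shortfall (days) |
|---|---|---|---|
| No ongoing AE or SAE at EOT | 30 | 91.3 | 182.6 − 91.3 = 91.3 |
| AE settled at first follow-up | 30 + 42 = 72 | 91.3 | 91.3 |
| AE settled at second follow-up | 30 + 84 = 114 | 114 | 182.6 − 114 = 68.6 |
| AE settled at third follow-up | 30 + 126 = 156 | 156 | 182.6 − 156 = 26.6 |
| Followed to 6 months | 182.6 | 182.6 | 0 |

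**Step 3: trial-level reading.** Let T be the days from the man's last dose to the last follow-up in the trial. The window is max(T, 91.3). There is no shortfall if T is at least 182.6. A gap remains only for men last dosed less than 6 months before the trial's final follow-up, and it is again at most 91.3 days.

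**Step 4: women.** The floor is 182.6 days and the contraception period after the last dose is 182.6 days, so the shortfall is 0.

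**Step 5: after the change.** With a 6-month floor the male window is max(E or T, 182.6), which is at least 182.6 days on either reading, so the shortfall is 0. This compares durations only. If a pregnancy is recognised L days after conception, the latest conception certain to be reportable is day 182.6 − L. The last L days of the contraception period stay uncovered, exactly as for women. The documents do not give L.

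**Step 6: other routes.**
- Special situation reports include pregnancy (Section 10.2.1.3) but run only for the duration of the study (Section 10.2.2.4), so they raise the same question of reading.
- Section 10.2.5 requires all pregnancies to be reported within 24 hours of awareness and sets no end date.
- Section 10.2.4 keeps SAEs that are adverse pregnancy outcomes reportable after the study.
- Section 10.2.2.3 covers late SAEs judged relevant to study drug, without a duty to seek them. A congenital anomaly in the child of an exposed subject is an SAE criterion (Section 10.2.1.2).

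The last three routes all require that the investigator hear of the event.

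**The case against.** **The two periods need not be equal.** Contraception and reporting are separate rules, and the 3-month figure is the same in both places it appears, so it may be a chosen floor. This stands: the reporting rule does not contradict itself, and nothing shows a slip. But no reason is given for the shorter male figure, and the female rules align the periods.

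**The gap depends on a reading.** On the trial-wide definition in Section 3.6, a man is covered for as long as the trial stays open. This also stands. The per-subject reading is better supported, because Section 5.4, footnote b and the individual EOS visit all end participation subject by subject. Section 10.2.4 also describes the study period by reference to Safety Follow-up visits, which men without ongoing events do not have. Still, the protocol does not settle the matter.

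**Serious outcomes remain reportable.** They do, once known. The weakness is that, on the per-subject reading, a man past both EOS and month 3 has no stated duty to tell anyone.

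**The harm is thin.** The protocol calls seminal exposure only a theoretical possibility. Mean half-lives are 19.7 hours for free SN-38 and 15.3 hours for sacituzumab govitecan (Section 1.3.1.3), so 3 months is 91.3 × 24 / 19.7 = 111 and 91.3 × 24 / 15.3 = 143 half-lives. This stands, and it limits the point to consistency of reporting.

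A reader might go further and infer that partner pregnancies in months 4 to 6 are unreportable for every man, or that fetuses are exposed in those months. The documents support neither. The first fails for men still in follow-up and, on the trial-level reading, for most men while the trial stays open; Section 10.2.5 also has no end date. For the second there is no evidence at all. The opposite shortcut, that any man with an ongoing AE at EOT is covered to 6 months, fails too on the per-subject reading, because his follow-up stops once the AE settles.

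**Conclusion.** The point holds as a minor correction to safety reporting. Read per subject, the partner-pregnancy window is shorter than the condom period for two groups: men with no ongoing AE or SAE at EOT, and men whose ongoing events resolve or stabilise so that they meet EOS before month 6. The shortfall is about 91 days for a man whose EOS falls in the first 3 months, and shrinks to zero as EOS approaches month 6. Read at trial level, it touches only men last dosed within 6 months of the trial's final follow-up.

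The number of men affected is unknown, because the documents give no male share, and such pregnancies would be rare. Nothing in the primary endpoints, analysis population or sample size changes. The conclusion rests on the text of the protocol and on the definition of childbearing potential excluding men; it does not rest on any assumed drug exposure.

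**What to change.** At the next amendment, change 3 months to 6 months in two places: the partner-pregnancy paragraph of Section 10.2.4, and the male-subject paragraph of Appendix 4 item 5. Make the same change in the consent form if it states 3 months; its text is not available here. The result matches Appendix 4 item 3 and the female rule, and sets a 6-month floor whichever way *throughout the study* is read.

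The cost is two numerals, a longer self-report duty for men and a longer reporting duty for investigators. No visits are added, so men who have reached EOS would still be covered by self-report alone. Pregnancies conceived late in month 6 and recognised afterwards could still fall outside, as they can for women.
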